#### 5.1.1.1.4 Missing Data

General missing data handling conventions are specified for methodologies in Section 5.1.1.1.3 and summarized as follows:

**Table 5-4 Missing Data Handling by Endpoint Type**

Endpoint type	Timing	Missing Data Handling
Responder	Treatment Period	
 
• All subjects included
 
• Subjects with no postbaseline values will be excluded
 

CFB ANCOVA	Treatment Period	
 
• If missing covariates (including baseline if applicable) 
 
○ Subject excluded
 
 
 
• If missing weighted average change from baseline UNVA letters: 
 
○ Subject excluded
 
 
 

CFB MMRM	Treatment Period	
 
• If missing covariates (including baseline if applicable) or missing values at all postbaseline analysis visits 
 
○ Subject excluded
 
 
 
• If missing weighted average change from baseline UNVA letters: 
 
○ Subject excluded
 
 
 

CFB Posebaseline	Treatment Period	
 
• If missing value at the specified postbaseline analysis visit: 
 
○ Available cases 
 
▪ Subject excluded
 
 
 
 
 

#### 5.1.1.1.5 Site Pooling

Data from all sites will be pooled for analysis.

#### 5.1.1.1.6 Other Common Conventions

Ocular adverse events and other ocular evaluations will be summarized using eye as the experimental unit by dosing group and dosing period. Nonocular adverse events and other nonocular assessments will be summarized using patient as the experimental unit by dosing group and dosing period.

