		10.5.2 Clinical Supply Inventory	
		10.5.3 Return or Disposal of Study Medications/Treatments and/or Supplies	
	10.6	Monitoring by the Sponsor	
	10.7	Publications	. 63

10.8	Coordinating Investigator	64
	ences	
12. Attach	nments	67
12 10 (Glossary of Abbreviations	91
	Protocol Amendment 1 Summary	
	Protocol Amendment 2 Summary	
	Protocol Amendment 3 Summary	
	Protocol Amendment 4 Summary	
	List of Tables	
Table 1	Study Treatment Groups	9
		64 67 91 93 97 98 98
	List of Figures	
Figure 2	Oxford Scale for Grading Corneal and Conjunctival Staining	86
Figure 3	Anterior Chamber Angle Grading	88

Protocol Summary

Study Compounds: AGN-199201 (oxymetazoline hydrochloride ophthalmic solution) AGN-190584 (pilocarpine hydrochloride ophthalmic solution) Phase: 2 Study Objective: To identify the optimum concentrations of AGN-199201 and AGN-190584 when dosed in combination once a day for the improvement of uncorrected near visual acuity (UNVA) in patients with presbyopia

Clinical Hypotheses:

At least one concurrently dosed combination of AGN-199201 and AGN-190584 will:

- demonstrate a significant improvement in UNVA over monotherapy with AGN-199201 and monotherapy with AGN-190584 when they are dosed at the same concentrations as the combination
- produce safety and tolerability findings no worse than cumulative findings with AGN-199201 monotherapy and AGN-190584 monotherapy when they are dosed at the same concentrations as the combination

Study Design

Structure: Multicenter, double-masked, randomized, vehicle-controlled

Duration: 39 to 112 days per patient

Study Treatment Groups: Patients will receive AGN-199201 and:

Group 1: AGN-190584 vehicle

Group 2: AGN-190584 ophthalmic solution,

Group 3: AGN-190584 ophthalmic solution,

Group 4: AGN-190584 ophthalmic solution,

All patients will receive the fixed combination of AGN-190584 ophthalmic solution and AGN-199201 ophthalmic solution during one of the 5 dosing periods. See Table 1 for details of the dosing groups.

Table 1 Study Treatment Groups

Group		Dominant eye		
	Unfixed Combination(s)		Fixed Combination	
1	AGN-199201,	AGN-190584, 0% (vehicle)	(AGN-190584, AGN-199201,) + Vehicle	Vehicle + Vehicle
2	AGN-199201,	AGN-190584,	(AGN-190584, AGN-199201,) + Vehicle	Vehicle + Vehicle
3	AGN-199201,	AGN-190584,	(AGN-190584, AGN-199201,) + Vehicle	Vehicle + Vehicle
4	AGN-199201,	AGN-190584,	(AGN-190584, AGN-199201,) + Vehicle	Vehicle + Vehicle

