Safety measures will be analyzed using the safety population. Medical Dictionary for Regulatory Activities (MedDRA) nomenclature will be used to code adverse events. Incidence rates of each treatment-emergent adverse event will be summarized by primary system organ class and preferred term. Treatment-emergent adverse events are events that occur or worsen after the treatment. Summary tables will be generated for all treatment-emergent adverse events regardless of causality as well as for those considered to be treatment-related. The adverse events will be classified into ocular and nonocular types and will be summarized separately as described below. Ocular adverse events and other ocular evaluations will be summarized using eye as the experimental unit by dosing group and dosing period. Nonocular adverse events and other nonocular assessments (eg, vital signs) will be summarized using patient as the experimental unit by dosing group and dosing period.

Detailed descriptions of the safety analyses for adverse events and other safety measures will be documented in analysis plan.

Sample Size Calculation:

The study consists of 4 parallel groups and 5 sequences of 2-day dosing periods within each group (see Figure 1). Each dosing period is separated by a washout of 14 ± 7 days and each sequence is tested 8 times resulting in 40 patients per group.

The sample size is deemed appropriate to build a response surface model that assesses the efficacy profile of the combination relative to monotherapies.

1. Background and Clinical Rationale

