1.4 Rationale for Study Design

Allergan Study 199201-007 achieved proof-of-concept for the current approach of treating presbyopia with a combination of oxymetazoline and pilocarpine ophthalmic solutions. This phase 2 clinical study is a systematic dose-response study designed to identify the optimum concentrations of oxymetazoline HCl (0.0125%, 0.05%, or 0.125%) and pilocarpine HCl (0.5%, 1%, or 1.5%) ophthalmic solutions dosed in combination for the improvement of UNVA in patients with presbyopia.

The results from Study 199201-007 suggest that pilocarpine improves UNVA in patients with presbyopia by decreasing pupil diameter which increases depth of focus. Oxymetazoline may further modulate the miotic effect of pilocarpine on UNVA by increasing both accommodation and duration. Study 199201-009 was designed to have more sensitivity to change in oxymetazoline concentration (ie, within patient comparison) than pilocarpine concentration (ie, between patient comparison). Secondarily, the current study brackets the concentration of pilocarpine used in 199201-007, the higher concentration of pilocarpine in the current study may result in a greater discontinuation rate. Thus, pilocarpine was selected as a between-patient variable to minimize any potential impact of patient discontinuation.

This study was designed to dose in the nondominant eye of younger presbyopic patients based on the results of 199201-007, as the greatest improvements in UNVA were seen with these two conditions. Due to the large number of comparisons when crossing over two drugs

each with 3 concentrations as well as monotherapies, it is not practical to use fixed combinations for all dose combinations in the current study. A fixed combination of pilocarpine 1% and oxymetazoline 0.125% was selected as the only fixed combination to enable bridging between the fixed combination used in this study and the unfixed combination used in this study and 199201-007.

Rationale for Dose Range

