2.2 Clinical Hypotheses

[figure not shown]
At least one concurrently dosed combination of AGN-199201 and AGN-190584 will:

- demonstrate a significant improvement in UNVA over monotherapy with AGN-199201 and monotherapy with AGN-190584 when they are dosed at the same concentrations as the combination
- 2. produce safety and tolerability findings no worse than cumulative findings with AGN-199201 monotherapy and AGN-190584 monotherapy when they are dosed at the same concentrations as the combination

3. Study Design

This study is a phase 2, multicenter, double-masked, parallel-group, randomized sequence, dose response, vehicle-controlled study in patients with presbyopia. Four groups (see Table 1) of different concentrations of AGN-190584 will be used to compare unfixed combinations with AGN-199201 and a fixed combination of AGN-190584 and a fixed combination of AGN-190584 and AGN-199201 solutions dosed in the nondominant eye during 5 dosing periods. For all 4 treatment groups, each dosing period will be once daily for 2 consecutive days, followed by a 7 to 21 day washout before the next 2-day dosing period, until exit after the fifth 2-day dosing period. The study duration will be 39 to 112 days per patient.

Following a screening visit (days -18 to -1) patients will be randomized at a baseline visit (visit 1) in a 1:1:1:1 ratio (stratified by the UNVA at baseline of $\leq 20/80$ and > 20/80) to 1 of the following treatment groups (also summarized in Table 1):

All patients will receive the fixed combination of AGN-199201 and AGN-190584 ophthalmic solutions within one of the 5 dosing periods. Vehicles for AGN-190584, AGN-199201, and the fixed combination ophthalmic solutions all have the same formulation.

Study medication will be administered once daily in each eye during office visits at hour 0 (8 AM \pm 1 hour) for 2 consecutive days during each dosing period. Dosing periods will be separated by a washout period of 14 ± 7 days. Eyes receiving both AGN-199201 and AGN-190584 are to receive a single drop of AGN-199201, followed approximately 5 to 7 minutes later by a single drop of AGN-190584. Eyes receiving the fixed combination of AGN-190584 and AGN-199201 are to receive a single drop of the fixed combination drug, followed approximately 5 to 7 minutes later by a single drop of vehicle. Eyes receiving vehicle alone are to receive 2 drops of vehicle, separated by approximately 5 to 7 minutes. The study design is depicted in Figure 1.

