5.4 Treatment Allocation Ratio and Stratification

Patients will be randomized in a 1:1:1:1 ratio into 1 of 4 treatment groups:

All patients will receive the fixed combination of AGN-190584 ophthalmic solution and AGN-199201 ophthalmic solution within one of the 5 dosing periods. The order of the dosing sequence in each group is shown in Table 3.

Patients will be stratified by UNVA at baseline of $\leq 20/80$ and > 20/80. For determination of stratification group assignment for each patient, sites will be required to enter the UNVA at baseline into the interactive response system (IxRS), and the IxRS will assign the stratum.

[figure not shown]

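### Does the undefined term 'dosing group' in SAP 5.1.1.1.6 leave safety tables that mix treatments?

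*SAP*

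**What the plan says.** SAP Section 5.1.1.1.6 (Other Common Conventions) states: "Ocular adverse events and other ocular evaluations will be summarized using eye as the experimental unit by dosing group and dosing period". It treats nonocular data in the same way, with the patient as the unit. Both sentences come from the safety part of the Protocol Summary, where the second reads: "other nonocular assessments (eg, vital signs) will be summarized using patient as the experimental unit by dosing group and dosing period". The same paragraph of the Protocol Summary adds: "The adverse events will be classified into ocular and nonocular types and will be summarized separately as described below".

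The visible SAP uses *dosing group* only in Section 5.1.1.1.6. The protocol gives the term content in one place, the treatment group part of the Protocol Summary: "See Table 1 for details of the dosing groups". Table 1 lists Groups 1 to 4. Protocol Section 3 describes them thus: "Four groups (see Table 1) of different concentrations of AGN-190584 will be used to compare unfixed combinations".

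Other SAP sections use different terms:

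- Section 5.1.1.1.2 defines the treatment groups as a list of 17 treatments.
- Section 4.1, the design summary, uses *treatment groups* for Groups 1 to 4.
- Table 5-1 bases the Safety population on the treatment actually received. Protocol Section 7.1 likewise analyses safety as treated.
- Section 5.1.1.4.2 counts unique subjects with adverse events, by treatment group and overall. It names no eye unit and no period.
- Table 5-23 counts an event from the treatment start date up to the end of the washout before the next dosing period, or to 30 days after the last dose.

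**The concern.** The protocol's groups are not treatments. Section 1.4 says the design gives "more sensitivity to change in oxymetazoline concentration (ie, within patient comparison) than pilocarpine concentration", so pilocarpine differs between groups and oxymetazoline varies within each patient. Every patient also receives the fixed combination once, including Group 1, whose pilocarpine component is vehicle. If *dosing group* means Groups 1 to 4, a column headed Group 1 would contain patients on a product with active pilocarpine.

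The second clinical hypothesis compares the safety of a combination with that of its two monotherapies at the same concentrations. Each unfixed combination shares a group with its pilocarpine monotherapy, so tables by Groups 1 to 4 could not show that comparison.

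The SAP also seems to give two rules for the same events. Section 5.1.1.1.6 counts eyes for ocular events, by dosing group and period. Section 5.1.1.4.2 counts subjects by treatment group, and the visible Table 5-21 does not separate ocular from nonocular events.

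**Working it through.** **Inputs.** Three active oxymetazoline and three active pilocarpine concentrations (Protocol 1.4); four groups, five sequences per group, eight patients per sequence (Protocol 7.5); 17 treatments (SAP 4.1 and 5.1.1.1.2); fixed combination once per patient (Protocol 3); dropout 12.5% (Protocol 4.1) or 10% (SAP 5.1.2).

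**1. Reproduce the plan's counts.** 5 × 8 = 40 patients per group and 40 × 4 = 160 in all, as stated. Treatments: 3 × 3 = 9 unfixed combinations + 3 + 3 monotherapies + 1 vehicle = 16, plus 1 fixed combination = 17, as stated. Each group therefore has 16/4 = 4 unfixed treatments plus the fixed one, over five periods.

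**2. What the Groups 1 to 4 reading would produce.** There would be 4 × 5 = 20 group-by-period cells. Protocol Section 5.4 says: "The order of the dosing sequence in each group is shown in Table 3". That table is not shown, so two cases are given.

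- *Five different orders, nothing more assumed.* If the orders differ in only k periods, there can be at most k! of them. 2! = 2 is fewer than 5 and 3! = 6 is enough, so at least 3 periods per group are mixed: 3 × 4 = 12 of 20 cells.
- *Balanced orders (assumption).* All 20 cells are mixed, with 40/5 = 8 patients per treatment. An event rate of 10%, 20% or 30% on one treatment and zero on the other four would show as 2%, 4% or 6%.

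In Group 1, 40 of 40 × 5 = 200 planned patient-periods (20%) are on the fixed combination. All 9 unfixed combinations share a group with their pilocarpine monotherapy. The Groups 1 to 4 reading would therefore be a poor display.

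**3. Which reading the plan supports.**

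| Rule | Groups 1 to 4 | Treatment received |
|---|---|---|
| 17 treatment groups defined (SAP 5.1.1.1.2) | not used | used |
| Adverse events by treatment group (SAP 5.1.1.4.2) | only with the looser sense of SAP 4.1 | fits the analysis definition |
| Safety by treatment actually received (SAP Table 5-1, Protocol 7.1) | not decisive alone | fits |
| Onset window closes before next dosing period (SAP Table 5-23) | gives the period only | gives the treatment in that period |

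The last row matters most. Once an event is assigned to a dosing period, the patient's sequence gives the treatment. Taken with the list of 17, this leads to tables by treatment received.

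**4. What those tables contain.** 16 × 40 + 160 = 800 = 160 × 5 planned patient-periods, one treatment per column. If only completers are counted and dropout is spread evenly over groups, the denominators are 40 × 0.875 = 35 and 160 × 0.875 = 140 at 12.5%, or 36 and 144 at 10%. Dropouts still contribute the periods they attended.

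**5. Eye or subject.** Each patient receives each assigned treatment in one period only, and active drug goes only to the nondominant eye (Protocol Table 1). With the two eyes shown separately, a count of affected nondominant eyes on a treatment equals the count of subjects affected in that eye. Nothing visible says the eyes are pooled.

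**6. The 5.0% listing rule.** The choice of reading has no fixed direction of effect. Two subjects on the same unfixed treatment, with events in different periods, give 2/40 = 5.0% by treatment but 1/40 = 2.5% in each group-by-period cell. Two subjects in one group and one period, on different oxymetazoline levels, give 2/40 = 5.0% in the cell but 1/40 = 2.5% for each treatment. The common-event row of Table 5-21 itself refers to treatment group, without period.

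**The case for a change.** The strongest case for a change is that two visible SAP rules cover the same adverse events and do not agree. Table specifications should implement the SAP, not choose between its rules. Section 5.1.1.1.6 names ocular adverse events explicitly and also governs the other ocular and nonocular assessments, to which Section 5.1.1.4.2 does not apply. The clause in Section 5.1.1.1.3 that allows exceptions covers only the methodology definitions, and Section 5.1.1.4.2 does not say that it overrides anything. *Treatment group*, the term that should settle the matter, has two meanings in the SAP.

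Much of this stands as a comment on drafting. The term is undefined in the visible text, and a one-line definition would have been tidier. It does not show that wrong tables would result. Section 4.1 is a design summary, and its loose usage does not displace the formal list in the analysis section. Section 5.1.1.1.6 already gives separate rules for ocular and nonocular events; as a common convention it need not be repeated in each of the nine rows of Table 5-21, and it can be read as supplying the eye unit where the general method counts subjects. For the other assessments, the as-treated basis of the Safety population still applies.

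**Conclusion.** No change to the plan follows. This is a gap that analysts fill sensibly: an undefined term, carried over from the protocol, whose troublesome reading is disfavoured by the SAP's own treatment list, its as-received safety basis and its period-bound event window. On the disfavoured reading at least 12 of 20 cells would mix treatments, or all 20 if the orders are balanced. On the supported reading none do, and the planned denominators are 40 and 160. The visible adverse event tables are descriptive, so no test, efficacy result or data collection depends on the wording.

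The figure of 12 assumes that the five sequences in a group are different orders of its five treatments; the figure of 20 also assumes balance, because Protocol Table 3 is not shown. Parts of the SAP's safety section are redacted and table layouts are in a separate specification, so the column and eye layout may already be stated there. If it is not, writing down the meaning of *dosing group* would clarify the protocol's as-treated intent and would not change the analysis.

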5.5 Method for Assignment to Treatment Groups/Randomization

Prior to initiation of study treatment, each patient who provides informed consent will be assigned a patient number that will serve as the patient identification number on all study documents.

[figure not shown]
At the time of randomization on visit 1, eligible patients will be placed into 1 of 2 strata as described in Section 5.4, and they will be assigned to 1 of the 4 treatment groups, in a masked fashion based on the randomization scheme within the patient's stratum according to the order of enrollment. The IxRS will assign the next available randomization number for the appropriate stratum to the patient at the time the investigator requests randomization. The IxRS will report 2 medication kit numbers (one for nondominant eye and one for dominant eye) to use for each patient corresponding to the randomization number. The randomization scheme will be prepared by Allergan Biostatistics.

[figure not shown]
Study medication will be labeled with medication kit number, study number, and dominant or nondominant eye. Each medication kit (carton) will contain 2 multidose bottles of study treatment; 1 bottle will be labeled with an 'X' and 1 bottle will be labeled with a 'Y'. The study treatment in each bottle will be administered in sequence (a single drop from bottle X first, followed 5 to 7 minutes later by a single drop from bottle Y). The IxRS will provide the site with the specific medication kit number(s) for each randomized patient at the time of randomization (day 1 of the first dosing period) and on day 1 of each subsequent dosing period. Sites will assign study medication kits according to the IxRS instructions. Sites will receive the IxRS confirmation notifications for each transaction. All notifications are to be maintained with the study source documents.

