8.4 Visits and Associated Procedures

[figure not shown]
Evaluations should be performed by the same evaluator throughout the study whenever possible. If it is not possible to use the same evaluator to follow the patient, then evaluations should overlap (examine the patient together and discuss findings) for at least 1 visit.

The following section provides a list of procedures for each scheduled visit. All ophthalmic procedures should be performed for each eye, unless otherwise noted. Additional information on the examination procedures, equipment, and techniques for the measures listed in this section is presented in Section 6.3.

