### 4.1 Study Design Summary

This study is a phase 2b, multicenter, double-masked, parallel-group, randomized sequence, dose response, vehicle-controlled study in patients with presbyopia. Sixteen unfixed combination of AGN-190584 [REDACTED] and AGN-199201 ([REDACTED]) and a fixed combination of AGN-190584 [REDACTED] and AGN-199201 [REDACTED] solutions will be dosed in the nondominant eye during 5 dosing periods. For 17 different treatment combinations, each dosing period will be once daily for 2 consecutive days, followed by a 7 to 21 day washout before the next 2-day dosing period, until exit after the fifth 2-day dosing period. The study duration will be 39 to 112 days per patient.

Following a screening visit (days -18 to -1) patients will be randomized at a baseline visit (visit 1) in a 1:1:1:1 ratio (stratified by uncorrected near vision acuity at baseline of  $\leq 20/80$  and  $> 20/80$ ) to 1 of the following treatment groups:

- Group 1: AGN-199201 [REDACTED] and AGN-190584 vehicle 0%
- Group 2: AGN-199201 [REDACTED] and AGN-190584 ophthalmic solution [REDACTED]
- Group 3: AGN-199201 [REDACTED] and AGN-190584 ophthalmic solution [REDACTED]
- Group 4: AGN-199201 [REDACTED] and AGN-190584 ophthalmic solution [REDACTED]

All patients will receive the fixed combination of AGN-199201 [REDACTED] and AGN-190584 [REDACTED] ophthalmic solutions within one of the 5 dosing periods. Vehicle for AGN-190584, vehicle for AGN-199201, and the vehicle for fixed combination ophthalmic solution have the same formulation.

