**Table 5-23 AE Terms**

Term	Description
Treatment-emergent	An event that initially occurs or increases in intensity on or after the treatment start date, where: 

• Treatment start date <math>\leq</math> event start date <math>\leq</math> following washout period before the next 2-day dosing period or last dose date + 30 days

On-therapy	An event where: 

• Treatment start date <math>\leq</math> event start date <math>\leq</math> following washout period before the next 2-day dosing period or last dose date + 30 days

[figure not shown]
AEs, encompassing abnormalities and surgeries reported as occurring after the Screening Visit, will be coded using MedDRA version 19.0 or newer. Unique subjects reporting AEs in the

following AE categories will be summarized by treatment group and overall for the Safety Population as follows:

[figure not shown]

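### Ocular adverse events have two inconsistent counting rules, and neither separates the treated nondominant eye from the vehicle-only dominant eye

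*SAP*

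**What the plan says.** **Who receives what.** SAP 4.1 describes 16 unfixed combinations and one fixed combination, and says these "solutions will be dosed in the nondominant eye during 5 dosing periods". In Protocol Table 1 the dominant-eye column is vehicle followed by vehicle for all four groups. Both eyes are dosed: Protocol 5.5 has the randomization system report two kits per patient, "one for nondominant eye and one for dominant eye". Both are examined: Protocol 8.4 says "All ophthalmic procedures should be performed for each eye, unless otherwise noted".

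**First counting rule.** The Protocol Summary (Safety) says of adverse events: "The adverse events will be classified into ocular and nonocular types and will be summarized separately as described below". The rule that follows there is repeated in SAP 5.1.1.1.6: "Ocular adverse events and other ocular evaluations will be summarized using eye as the experimental unit by dosing group and dosing period". The Protocol Summary points to Table 1 for its dosing groups, which are the four parallel groups.

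**Second counting rule.** SAP 5.1.1.4.2 says that unique subjects reporting AEs in the "following AE categories will be summarized by treatment group and overall for the Safety Population". Every row of Table 5-21 uses categorical descriptives, which Table 5-3 (M2) defines as numbers and percentages of subjects. Table 5-21 has no row for eye and none for ocular against nonocular events.

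**Treatment columns.** SAP 5.1.1.1.2 lists 17 treatments. None is labelled as the vehicle given to the dominant eye.

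**The concern.** Each patient contributes one eye on the period's assigned treatment and one on vehicle. An ocular AE rate for a concentration pair is interpretable only if the event is tied to the eye that received that pair. Neither visible rule does this, and the two disagree on both the unit (eye or subject) and the column (dosing group by period, or treatment).

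The study exists to choose concentrations. The second clinical hypothesis (Protocol 2.2) compares the safety and tolerability of a combination with its monotherapies at the same concentrations. Eyelid retraction, an event of the eye region, was the exception to otherwise similar AE findings between groups in Study 199201-007 (Protocol 1.3). If ocular events are not tied to the treated eye, the comparison between a combination and its monotherapies can be flattened or contaminated, depending on which rule the programmer follows.

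**Working it through.** **Inputs from the documents.** Protocol 7.5: 5 sequences, each used 8 times, in each of 4 groups. Protocol Table 1: dominant eye always on vehicle. Protocol 5.5 and 8.4: two dosed and examined eyes per patient.

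**Inputs assumed.** The documents give no ocular AE rate for this trial. Take a treated-eye rate pT of 10% or 20%, a vehicle-eye rate pV of 0% to 5%, and independence between eyes for the subject count.

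**The plan's own figure.** 5 × 8 = 40 patients per group; 40 × 4 = 160 in total. Both reproduce.

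**Rule 1 as written, by dosing group and dosing period.** At full enrolment a cell has 40 patients and 40 × 2 = 80 eyes.
- Dominant, vehicle-only: 40.
- Nondominant: 40, spread over five treatments. If each sequence supplies a different treatment in each period, that is 40 / 5 = 8 eyes per treatment.
- Any one treatment therefore accounts for 8 / 80 = 10% of the eyes in the cell.

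Such a cell gives no rate for any concentration pair.

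**Rule 1 read by treatment, both eyes pooled.** Shown rate = (pT + pV) / 2. For pT = 20%:

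| pV | Shown rate |
|---|---|
| 0% | (20 + 0) / 2 = 10.0% |
| 2% | (20 + 2) / 2 = 11.0% |
| 5% | (20 + 5) / 2 = 12.5% |

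A difference of 20% against 10% shows as 5 points at any common pV, because pV cancels and the divisor of 2 remains. If pV equals pT there is no dilution.

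**Rule 2, unique subjects by treatment.** Shown rate = 1 − (1 − pT)(1 − pV). For pT = 10%:

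| pV | Shown rate |
|---|---|
| 0% | 1 − 0.90 × 1.00 = 10.0% |
| 2% | 1 − 0.90 × 0.98 = 11.8% |
| 5% | 1 − 0.90 × 0.95 = 14.5% |

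The rate is never diluted; it rises because dominant-eye events are charged to the active treatment. A difference of 20% against 10% is multiplied by (1 − pV), so at pV = 5% it is 10 × 0.95 = 9.5 points.

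**With the eyes separated.** Counting nondominant eyes only, pT = 20% stays 20% on 40 eyes per unfixed treatment at full enrolment.

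**The case against.** The strongest reply is that pooling appears nowhere in the text. The eye is the unit and the safety population is analysed as treated (Protocol 7.1, SAP Table 5-1), so a careful programmer could place each eye under what it received. Protocol 1.4 lists three active concentrations of each drug, which with vehicle of each makes 4 × 4 = 16 unfixed combinations. One of these is therefore vehicle with vehicle, and dominant eyes could be tabulated there because all vehicles share one formulation. Large parts of the SAP safety section are redacted, and table specifications sit in a separate document. The visible AE summaries are descriptive, with no safety margin. The two distortions are also alternatives, and the subject count barely changes differences between treatments.

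Much of this stands. A reader might infer that the SAP prescribes pooling and that ocular rates will be halved; the text is silent on pooling, and halving needs both pooled eyes and a vehicle-eye rate of zero. A reader might also infer that no ocular evaluation is split by eye; redaction prevents that conclusion. Nor do the documents support using brow ache as an example, since Protocol 1.1 describes it as headache and nothing classes it as an eye-level event. It also cannot be said that patients know the dominant eye gets vehicle, since Protocol 5.3 describes full masking.

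The reply does not remove the conflict. Table 5-21 is visible, counts subjects and has no eye split. Placing dominant eyes in the vehicle column is workable but unstated. It would combine up to 160 × 5 = 800 dominant-eye periods with the 40 nondominant eyes of the double-vehicle treatment, so it should be decided rather than left to programming.

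**Conclusion.** The point holds as an inconsistency and an omission. The plan gives two rules for ocular AEs that differ in unit and column, and neither separates the treated eye from the vehicle-only eye. Followed literally, neither yields a clean ocular AE rate per concentration pair, which the second clinical hypothesis needs.

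The size depends on how the rules are executed. Pooling within a treatment would roughly halve rates and halve differences when vehicle-eye rates are low and common to the treatments. Subject counting would add a few points to every column and leave differences nearly intact. These magnitudes rest on assumed rates, and the subject figures also on independent eyes. The 8-per-treatment figure rests on balanced sequences and full enrolment. The conclusion covers the visible AE tables; it does not extend to redacted ocular evaluations. The change should be made before database lock.

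**What to change.** Align the Protocol Summary (Safety), SAP 5.1.1.1.6, SAP 5.1.1.4.2 and Table 5-21 on one rule. If the protocol is not amended, record the clarification in SAP 5.2.2.

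- Tabulate ocular AEs and ocular evaluations for the nondominant eye under the treatment given in that period, with the number of patients dosed with that treatment as denominator.
- Show dominant (vehicle) eyes separately, not merged into any active column.
- Count a bilateral event once in each eye's table.
- Add the ocular and nonocular split to Table 5-21, and keep patient-level counting for nonocular AEs.

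The cost is SAP wording and table shells. No new data are needed provided AE laterality is recorded, which counting by eye already presumes; this should be confirmed against the case report form.
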